changes in gene and protein expression in PBMCs. In fact, three recent studies used procedures very similar to those proposed in this application and deserve a more thorough review including the observed effect sizes (expressed as Cohen's  $d$ ). One of these studies was focused on the effects of MBI on cytokine production in PBMCs without a lipopolysaccharide (LPS) challenge (Witek-Janusek et al., 2008). In this study, an 8-week MBSR intervention ( $n=38$ ) was compared to a control intervention ( $n=28$ ) in a sample of breast cancer survivors. The results indicated that MBSR resulted in significantly lower levels of inflammatory cytokines in PBMCs across the trial (IL-4,  $d=.89$ ; IL-10,  $d=.55$ ). The effects were most pronounced immediately after the intervention and at the 4-week follow-up. There was no effect on IL-6. Another study examined the acute effects of a mindfulness meditation condition ( $n=19$ ) versus a control condition ( $n=21$ ) on expression of genes involved in epigenetic regulation (i.e., HDAC inhibitor genes) and inflammatory pathways in PBMCs (Kaliman et al., 2014). In this study, mindful meditation produced robust changes in genes involved in epigenetic regulation (HDAC2,  $d=.71$ ; HDAC3,  $d=1.0$ ; HDAC9,  $d=.92$ ) and pro-inflammatory genes (RIPK2,  $d=.95$ ; COX2,  $d=.52$ ). Finally, the last study examined the effect of an MBI for the treatment of insomnia (Irwin et al., 2015). Unlike the first two studies, PBMCs were isolated and TLR4 receptors were stimulated with LPS before assaying for inflammatory markers. The MBI condition ( $n=48$ ), compared to the control condition ( $n=25$ ), reduced inflammatory biomarkers at 4 months (TNF $\alpha$ ,  $d=.59$ ; IL-6,  $d=.57$ ) and 7 months (TNF $\alpha$ ,  $d=.64$ ; IL-6,  $d=.64$ ) after the intervention. These studies were selected because they are most similar to the proposed study in terms of testing the effect of MBIs on immune system biomarkers in PBMCs. In all three studies, the effect sizes for the impact of MBIs on inflammatory biomarkers and epigenetic regulation ranged from moderate to large, indicating that MBIs may have strong effects on inflammation and epigenetic regulation. Finally, it is important to note that the last study described above is particularly relevant to the proposed work because it utilized LPS stimulation of TLR4 receptors, which is exactly the pathway that has been implicated in the development and maintenance of AUDs (see Figure 1 above). Thus, the proposed research will feature a vertically integrated assessment of epigenetic regulation, neurogenic inflammation including basal and LPS stimulated changes in inflammatory gene expression in PBMCs, immunoassays of cytokines in PBMCs, and downstream effects on structure and function of control circuits in the brain.

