### **MBRP and RP Implementation.**

Consistent with the treatment manuals and previously published papers, a goal of abstinence is encouraged but not required (see [name] et al., 2014). For scheduling logistics, we will not have a group format but instead each treatment will be provided individually. As noted in the budget justification, the consultants ([name] and [name]) along with [name] (Co-I), will be on-site at the inception of the study to provide feedback on the refinement and implementation of MBRP and RP. [name] and [name] will continue to provide expert supervision and consultation throughout the study. [name], who is widely known for her expertise with MBIs, will be onsite for supervision and training throughout the trial. Therapists will be selected from the graduate program in clinical psychology at the University of Colorado and will have a master's degree in clinical psychology and previous training in the fundamentals of psychological intervention provided by [name] or [name]. At the inception of the study, [name] will travel to Boulder to provide a two-day workshop on MBRP. At a separate time, [name] will travel to Boulder to provide a two-day workshop on RP. In advance of the training workshops, prospective therapists will study the relevant manual (MBRP or RP). The workshops will contain both didactic and role-play exercises. *Therapists will be cross-trained in the interventions and will lead an equal number of both conditions to prevent therapist effects.* After training, prospective therapists will be required to demonstrate competency in MBRP or RP by submitting audio recordings of pilot therapy sessions with patients recruited through the University of Colorado training clinic, who will not be part of the proposed study. The recordings will be reviewed by [name] and either [name] or [name] and rated using both the Yale Adherence and Competence Scale as well as the MBRP competence scale, using a 7-point Likert scale as described in previous reports ([name] et al., 2014). Therapists who demonstrate an average rating of 5 across the duration of the 8-week treatment will be certified to be a therapist for the trial. During the course of the trial, weekly supervision meetings will be convened and an on-site supervisor ([name] or [name]) will review at least one audio recording per week using the same rating scales to ensure consistency in the treatment throughout the duration of the trial. [name] will visit Boulder once per year to assess overall fidelity and progress of the trial. MBRP will consist of 8 weekly 1-hour sessions provided in an individual format, whereas RP will consist of the same format, time, location, and amount of assigned homework but will not contain the mindfulness content provided during MBRP.

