
Participants will be instructed to arrive at the CINC 10 minutes prior to their scheduled appointment and meet in Room 129. Participants will fill out a quick check-in survey on an iPad before their appointment begins in order to inform therapists of the extent to which they completed their home practice the week before. The check-in survey will also allow participants to record any questions they have for their therapist before the appointment begins. The room will have two chairs with a coffee table in between the chairs, along with meditation cushions. Water will be available in the room. At each session, the therapist will engage and guide the participant in a discussion and exercise. The session will last one hour.

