### **Specific Aim 3 - Mediational analyses.**

Mediational analyses based on structural equation modeling with latent variables will be used to examine the mechanisms by which MBRP has its effects on behavioral outcomes related to alcohol use and dependence (See Figure 4; HYPOTHESIS 4) (Baron & Kenny, 1986; [name] et al., 2007). Mediational analyses will utilize the methylation and inflammation data collected at 4 weeks, and changes in cue-elicited BOLD activation and network connectivity strength at 8 weeks as the mediators, and drinking outcome data collected at 20 weeks. The exogenous variable in the model is the contrast that compares MBRP to RP. Methylation, inflammation, and drinking outcomes are all conceptualized as latent variables, which means that they are not directly measured, but are rather inferred via the measurement of variables thought to be a consequence of the latent variable. Latent variables have advantages over measured variables in that they are more reliable and thus allow for higher power for the test of relationships between the underlying construct and other variables (Kline, 2010).

The model is then estimated in EQS, and both the fit of the model and the significance of the path coefficients are examined. If HYPOTHESIS 4 is supported, we will see significant paths from the treatment contrast to methylation and inflammation. Further, there will be significant paths from methylation to cue-elicited BOLD activation and from inflammation to network connectivity. Finally, we expect significant relationships between BOLD activation and network connectivity to drinking outcomes. Importantly, tests for the completeness of mediation of the treatment differences in drinking outcomes are employed through a one degree of freedom  $\chi^2$  test where a path directly from the treatment contrast to drinking outcomes is added to the model. A nonsignificant direct path and a nonsignificant change in  $\chi^2$  suggest that treatment effects on drinking outcomes were mediated through the series of molecular and brain-based mechanisms. A secondary test of mediation will utilize bootstrap methods to test the significance of, and confidence limits around, the mediated effect (Mackinnon & Dwyer, 1993). Similar mediational analyses have been widely used by Co-I [name] ([name] et al., 2007).

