### **Intermediate Session (4 weeks)**

At the intermediate session, subjects will continue with their usual session with a therapist (including a BAC test), and either before or after their appointment, complete a set of self-report outcome measures, and provide a blood sample. Subjects will be compensated \$30 for completion of this session.

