### **End of Treatment (8 weeks)**

At the end of treatment session, subjects will continue with their usual session with a therapist (including a BAC test), and either before or after their appointment, complete a set of follow-up outcome measures including questionnaires and neurocognitive tests, and provide a blood sample. Subjects will be compensated \$30 for completion of this session, plus an additional \$15 for completing each therapy session (weeks 1-3 and 5-7), for a total of \$90 if they have attended all 6 sessions. Participants will receive their second gut microbiome sample collection kits at the end of the session and will return them using a pre-paid, pre-addressed envelope that we will provide for them.

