### **Follow-up Assessment I (20 weeks)**

At this follow-up session, all subjects will take a BAC test, complete a set of self-report outcome measures and provide a blood sample. Subjects will be compensated \$50 for completing this assessment (\$30 for completing self-report measures and \$20 for providing blood samples). For subjects who are unable to come into the laboratory, the option of completing self-report measures online (via Qualtrics) will be provided for a \$30 compensation.

Participants who are unable to come into the laboratory will be sent an email, with an anonymous link to the same Qualtrics survey that would be administered at the follow-up assessments. All surveys are administered via Qualtrics and, thus, participants will already be familiar with navigating this online survey. The email will include the following instructions:

As our study staff noted, your progress since finishing treatment is extremely important for us to understand how alcohol treatments work, and why they may work better for some individuals than others. Therefore, regardless of whether you feel you have improved, declined, or had no changes since completing treatment, your responses are equally valuable. To reimburse you for your time, we will provide a \$30 gift card.

If you choose to proceed, here is the link to your survey: [INSERT LINK]

After clicking the link, please enter your study ID and treatment condition (see below). Please fill out this survey alone to ensure focus and anonymity. In addition, you may discontinue participation or refuse to answer any questions without penalty. Once you have completed the survey, study staff will be notified and you will receive your compensation within one week.

Your study ID is: [INSERT ID]

Your treatment condition is: [INSERT MBRP or RP]

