MBRP (or RP) Therapy Sessions (weeks 1-3 and 5-7)	
 
• BAC test; Mindfulness Relapse Prevention or Relapse Prevention therapy session with a trained therapist
 
	CINC	1 hour each session (6 hours total)
Intermediate Session (week 4)	
 
• BAC test; MBRP (or RP) therapy session; Questionnaires; Blood draw
 
	CINC	2 hours
End of Treatment Session (week 8)	
 
• BAC test; MBRP (or RP) therapy session; Questionnaires; Neurocognitive tests; Blood draw; receive microbiome kit
 
	CINC	2 hours
Mail-in Sample from Home	
 
• Subject will mail-in their collection kit back to our lab in a pre-paid, pre-addressed envelope.
 
	At Home	5 minutes

Follow-up Session (week 20)	
 
• BAC test; Questionnaires; Blood draw
 
	CINC	1 hour
Follow-up Session (week 32) & MRI Scan II	
 
• BAC test; Questionnaires; Blood draw; Pregnancy test; MRI scan
 
	CINC	1 hour (2 hours with scan)
Check-In Session (week 33)	
 
• BAC test; a check-in session with a therapist to discuss potential relapse.
 
	CINC	30 minutes
TOTAL TIME		Approximately 16 hours (18 hours with MRI)	

Due to the COVID-19 situation we are collecting remote data only and will return to our original protocol when it is safe to do so. The remote PROCEDURES will be as follows:

**BASELINE SESSION:** The first study appointment is an orientation and consent session, also referred to as the Baseline session. For this appointment, the participant will meet with a research assistant who will take them through the informed consent document and give them an opportunity to ask any questions about their participation in the study. The participant will show their ID over Zoom to the confirm they are between 21-60 years old. Then a research assistant will use Docusign to electronically sign the consent form and send it to the participant to sign. Signed consent forms will be stored securely on our server in a password protected folder.

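### In-person week-4 and week-8 samples and questionnaires may be taken before or after that day's therapy session, so inflammation and state measures can mix a short-lived post-session effect with the sustained treatment effect

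*Combined protocol and SAP*

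**What the plan says.** Section XI (Procedures), Intermediate Session (4 weeks): participants have that week's therapy session and, "either before or after their appointment, complete a set of self-report outcome measures, and provide a blood sample". End of Treatment (8 weeks) uses the same construction: "either before or after their appointment, complete a set of follow-up outcome measures including questionnaires and neurocognitive tests, and provide a blood sample". The in-person visit table at the end of section XI lists the week-4 components of a two-hour visit as "MBRP (or RP) therapy session; Questionnaires; Blood draw" and states no order rule.

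The other assessments involve no treatment session that day. At week 20, "all subjects will take a BAC test, complete a set of self-report outcome measures and provide a blood sample", and week 32 is worded alike. The baseline visit precedes all therapy.

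On session content, section IV says "At each session, the therapist will engage and guide the participant in a discussion and exercise". The RP sessions match in format and time but "will not contain the mindfulness content provided during MBRP".

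On use of the data, the Aim 2 analysis puts IL-6, IL-8 and TNF-alpha at baseline and weeks 4, 8, 20 and 32 into one treatment-by-time model. For Aim 3, "Mediational analyses will utilize the methylation and inflammation data collected at 4 weeks".

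The background section on treatment targets says "Another study examined the acute effects of a mindfulness meditation condition" against a control condition, and reports d=.71, 1.0 and .92 for HDAC2, HDAC3 and HDAC9, and .95 and .52 for RIPK2 and COX2, all expression in PBMCs.

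In the remote (COVID-19) phase no blood or neurocognitive data are collected. The remote text for weeks 4 and 8 mentions the therapist meeting and the questionnaires without saying which comes first.

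**The concern.** A blood sample drawn just before the fourth session reflects about a week since the last one. A sample drawn just after it also reflects whatever an hour of guided practice does in the short term. The protocol lets both count as the week-4 value. Because only one arm's sessions contain mindfulness content, and the protocol's own background cites short-term effects of meditation on gene expression in PBMCs, any post-session shift is plausibly larger under MBRP.

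What is at stake is interpretation of the inflammation results. The week-4 inflammation measure is meant to stand for a change that goes on to influence network connectivity and then drinking. A same-day shift that fades would contribute to the treatment-to-inflammation path without being that change. Weeks 4 and 8 would also differ from baseline, week 20 and week 32 in time since the last session, which complicates reading the treatment-by-time pattern. State self-reports, such as urge to drink on the AUQ, have the same weakness.

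**Working it through.** The plan gives no figure on this point to reproduce. The check has three parts.

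**1. Time points side by side (in person)**

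| Assessment | Same-day MBRP or RP session | Order of assessment and session |
|---|---|---|
| Baseline | No | Not applicable |
| Week 4 | Yes | Either |
| Week 8 | Yes | Either |
| Week 20 | No | Not applicable |
| Week 32 | No | Not applicable |

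No section says that order is fixed, randomised, recorded or adjusted for. The covariate rule in the Data Analysis Plan concerns only variables on which the arms differ at pretest.

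**2. Which measures are exposed**

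- Heavy drinking days come from the TLFB, recalled over the previous 30 days. One hour of therapy does not materially alter that count.
- Liver tests: a same-day session has no material bearing on them.
- DRD2, SLC6A3 and DBH methylation: the documents offer no evidence of a shift within an hour. The acute results cited are for gene expression.
- IL-6, IL-8 and TNF-alpha, and the LPS-PBMC cytokine protein and mRNA levels: exposed. The first three are the Hypothesis 2 inflammation outcomes.
- State self-reports (AUQ) and week-8 neurocognitive tests: exposed, but in no model named for Aims 1 to 3.

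**3. Illustrative size**

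Inputs:
- p, the share of MBRP draws taken after the session: not in the documents; assumed, range 0 to 1.
- d_a, the acute effect under MBRP: .52 to 1.0, the range cited in the background. It comes from other genes and from a comparison of 19 with 21 people; the study's title in the reference list says expert meditators.
- Acute effect under RP: assumed 0.
- Sustained effect: set to 0, to isolate the same-day part.

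The MBRP mean shifts by p × d_a, and mixing pre- and post-session samples adds p(1−p)d_a² to the MBRP variance. With unit variance otherwise,

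apparent d = p·d_a / √{[2 + p(1−p)·d_a²] / 2}.

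- p=.5, d_a=.52: .26 / √(2.0676/2) = .26 / 1.017 = .26.
- p=.5, d_a=1.0: .50 / √(2.25/2) = .50 / 1.061 = .47.
- p=.25, d_a=.52 to 1.0: .13 to .24.
- p=.5, d_a=.20: .10.
- p=0 (all draws before the session): 0.

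If both arms had the same acute effect, it would cancel unless the order mix differed by arm. A 20-point difference in the mix would give .20 × .52 = .10 to .20 × 1.0 = .20.

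For scale, the Aim 3 power section assumes d=.60 for the effect of MBRP on inflammation and epigenetics, from a literature review that includes the acute study. The planning value therefore does not separate acute from lasting effects either.

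**The case against.** The strongest reply is that a post-session shift in the MBRP arm is still caused by randomised MBRP. That is right. A reader might infer that the arm difference would be spurious, but the documents do not support this: the contrast remains randomised, and Hypothesis 2 is worded as a decrease with treatment, without an explicit requirement that it persist. The issue is which effect is measured, acute or sustained. Weeks 20 and 32, with no same-day therapy, also give the Aim 2 model a chance to show a purely transient effect as transient.

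A reader might also infer that the trial's main comparison or the methylation mediator is compromised. Neither follows, given the 30-day recall and the absence of any evidence on rapid methylation change.

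Nor is it established that the Aim 3 indirect effect would be inflated. Transient variation could enlarge the treatment-to-inflammation path yet weaken the path from inflammation to connectivity; the net direction is unknown.

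Finally, the cited effect sizes are borrowed. They concern genes that are not Hypothesis 2 outcomes, in experienced practitioners, while this exposure is a one-hour session of discussion and exercise. RP may have an acute effect of its own. This stands, and it is why the figures above are illustration only. What remains is that the protocol expressly permits either order at the visit that supplies the Aim 3 mediators, for no stated reason beyond scheduling latitude.

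**Conclusion.** The concern holds in a limited form. For in-person participants, the order of assessment and therapy at weeks 4 and 8 is left open, and the inflammation measures and state self-reports at those visits may combine a short-lived post-session effect with the sustained one. The week-4 inflammation mediator is the most important use affected.

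The documents do not allow the size to be derived. Under p=.5, no acute effect in RP, and an acute effect equal to the cited d=.52 to 1.0, the apparent arm difference is about d=.26 to .47. It falls roughly in proportion with a smaller share or a smaller acute effect, and is zero if every draw precedes the session. The primary outcome and the liver tests are not materially affected, and there is no evidence in the documents that methylation is. The change is worth making because it is cheap and removes an avoidable ambiguity, not because a large bias has been shown.

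**What to change.** - In section XI, Intermediate Session (4 weeks) and End of Treatment (8 weeks), replace the before-or-after clause with: *before that day's therapy session, after the breath test*. Apply it to both arms, and record the draw time and the session start time.
- In the remote procedures for weeks 4 and 8, add a sentence that questionnaires are completed before the therapy session. The remote visits have no blood, breath or neurocognitive step, so nothing else changes there.
- Where order has already varied and times can be recovered, report the week-4 and week-8 inflammation results with draw order as a covariate, or in pre-session samples only. Label this a sensitivity analysis and state that order was not randomised. The documents do not mention recorded draw or session times, so this may not be possible for everyone.

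The cost is less flexible booking at two visits; no extra participants, assays or visits are needed. The change does not remove every acute influence, because home practice is assigned and a participant may practise earlier the same day.

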### **End of Treatment (8 weeks)**

At the end of treatment session, subjects will continue with their usual session with a therapist (including a BAC test), and either before or after their appointment, complete a set of follow-up outcome measures including questionnaires and neurocognitive tests, and provide a blood sample. Subjects will be compensated \$30 for completion of this session, plus an additional \$15 for completing each therapy session (weeks 1-3 and 5-7), for a total of \$90 if they have attended all 6 sessions. Participants will receive their second gut microbiome sample collection kits at the end of the session and will return them using a pre-paid, pre-addressed envelope that we will provide for them.

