### **Specific Aim 1.**

#### Comparing the effectiveness of MBRP (n=113) to RP (n=113).

- Hypothesis 1. It is hypothesized that MBRP will demonstrate superior effectiveness, as compared to RP, by reductions in heavy drinking days at the end of treatment (8 weeks) and longer term (20 and 32 weeks) decreases in liver function tests (8, 20, and 32 weeks).

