#### **Specific Aim 1 - Detecting Treatment Effects on Drinking Outcomes.**

The effect of the treatment on alcohol use outcomes (HYPOTHESIS 1) will be analyzed with a 2 (**Treatment:** 8 weeks of MBRP vs. 8 weeks of RP) x 5 (**Time:** Baseline, 4, 8, 20, 32 weeks) mixed general linear model with Heavy Drinking Days (HDD) as the primary outcome variable. We will also examine drinks per drinking day, ICS score, and liver function tests as dependent measures in each of 2 additional models, respectively. In the main analysis with HDD, a significant overall test of the treatment X time interaction will be followed by planned contrasts within the mixed model that allow us to test the superiority of MBRP over RP at the 8, 20, and 32 week follow-up points specifically. The FIML estimation procedure implemented in these analyses will allow us to utilize an “intent to treat” approach such that all subjects who are randomized will be included in the analyses (Schafer & Graham, 2002). It may be that the treatments are equally effective on drinking outcomes, and thus we will not see a direct effect of treatment on outcomes. Even in this case, it is possible that the mechanisms through which the treatments had their impact may differ. Thus, tests of Specific Aims 2 and 3 are still important and warranted.

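### Week-4 and week-8 outcomes are described only as part of that week's therapy appointment, so participants absent from therapy have no documented way to give heavy drinking days at week 8

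*Combined protocol and SAP*

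**What the plan says.** Section XI (Procedures), End of Treatment (8 weeks), reads "At the end of treatment session, subjects will continue with their usual session with a therapist (including a BAC test" and continues "and either before or after their appointment, complete a set of follow-up outcome measures including questionnaires and neurocognitive tests". Intermediate Session (4 weeks) has the same structure: "At the intermediate session, subjects will continue with their usual session with a therapist (including a BAC test", then "and either before or after their appointment, complete a set of self-report outcome measures, and provide a blood sample". The visit table in section XI lists therapy and assessment as a single visit. Its week-4 row is "BAC test; MBRP (or RP) therapy session; Questionnaires; Blood draw", and the week-8 row adds the neurocognitive tests and the microbiome kit. In the temporary COVID-19 procedures a research assistant sends the questionnaires by link over Zoom, but weeks 4 and 8 remain combined with that week's therapy session.

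A remote alternative for non-attenders first appears in Follow-up Assessment I (20 weeks): "For subjects who are unable to come into the laboratory, the option of completing self-report measures online (via Qualtrics) will be provided". It is repeated for week 32. Section VIII (Compensation) matches this. Only weeks 20 and 32 have a survey payment that applies wherever the survey is done ($30, with a separate $20 for blood). Weeks 4 and 8 each carry one $30 payment for the session.

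On the analysis side, Hypothesis 1 under Specific Aim 1 judges superiority "by reductions in heavy drinking days at the end of treatment (8 weeks" and also in the longer term. The Data Analysis Plan for Specific Aim 1 plans HDD contrasts at weeks 8, 20 and 32. It uses full information maximum likelihood (FIML) as an intent-to-treat approach, "such that all subjects who are randomized will be included in the analyses". HDD comes from the Timeline Follow Back (TLFB), which asks about the previous 30 days.

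**The concern.** Data collection at weeks 4 and 8 is tied to the treatment whose effect is being measured. If staff follow the text as written, someone who has left therapy, or does not attend session 4 or 8, receives no instruction, survey link or separate payment for that assessment. HDD is the primary outcome, and week 8 is the first of its three planned superiority contrasts.

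FIML keeps such a participant in the model, but it predicts the missing week-8 value from baseline and later visits. It treats leaving therapy as carrying no further information about drinking at that time. If people who leave are drinking more, the all-randomised week-8 difference is misestimated. If MBRP and RP lose different proportions, the error can favour either arm.

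The attrition checks do not repair this. The comparison in The impact of attrition uses pretest alcohol measures, and the treatment-by-retention models in Differential attrition analyses use baseline measures. Neither sees drinking during treatment. The Data Analysis Plan also promises extensive attrition analyses, but names no method and no sensitivity analysis for departures from missing at random.

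**Working it through.** **1. The plan's own figure.** Power for Specific Aim 1 uses f = .10, correlation .50, five time points and N = 180. Then λ = N·m·f²/(1 − ρ) = 180 × 5 × .01 / .50 = 18, on 4 and 712 degrees of freedom. Power is .94 under sphericity, consistent with the stated figure of well over .90. For recruitment, 180/.80 = 225 against about 226 stated. The sample size reproduces. The 20% attrition behind it is for the whole data collection and is not specific to week 8.

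**2. Can a later visit supply the week-8 value?** The 30-day TLFB covers these days:
- week 8 (day 56): days 26–56
- week 20 (day 140): days 110–140
- week 32 (day 224): days 194–224

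The windows do not overlap, so it cannot.

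**3. Size of the bias.**

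Inputs from the documents: 113 per arm, correlation .50, and an effect of −.23 SD in those who stay (the low end of the previous-trial effects quoted in the power section).

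Inputs assumed, because the documents give none:
- no treatment effect in stoppers
- stoppers .5 SD worse at weeks 4 and 8, and .25 SD worse at weeks 20 and 32
- stoppers the same as stayers at baseline
- weeks 4 and 8 missing in stoppers, and all other visits observed.

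With compound symmetry at .50, week 8 is predicted from baseline, week 20 and week 32. Each coefficient is b = .50/(1 + 2 × .50) = .25.

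Let p be the proportion stopping in an arm, D8 the stopper-minus-stayer gap at week 8, and DL the gap at weeks 20 and 32.
- True arm mean = stayer mean + p·D8
- FIML expectation = stayer mean + p × .25 × (0 + DL + DL) = stayer mean + .5·p·DL
- Bias in the arm = −p(D8 − .5·DL)

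RP: D8 = .50 and DL = .25, so bias = −.375p. MBRP: D8 = .50 + .23 = .73 and DL = .25 + .23 = .48, so bias = −.49p. Bias in the MBRP − RP difference = −.49·p(MBRP) + .375·p(RP).

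| Stopping, MBRP / RP | True difference | FIML expectation | Bias |
|---|---|---|---|
| 15% / 15% | −.196 | −.213 | −.017 (9% too large) |
| 20% / 10% | −.134 | −.194 | −.060 (45% too large) |
| 10% / 20% | −.257 | −.231 | +.026 (10% too small) |

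First row in full: true = .85 × (−.23) + .15 × .5 − .15 × .5 = −.1955. FIML = (−.23 + .5 × .15 × .48) − (.5 × .15 × .25) = −.194 − .01875 = −.21275.

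Milder inputs (stoppers .25 SD worse at weeks 4 and 8, .125 SD worse later) reduce the 20%/10% bias from .060 to .042.

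**4. Precision.** With complete data, SE = √(2/113) = .133. With missing data, R² = 3 × .25 × .50 = .375. At 15% stopping in each arm, SE = √[(2/113)(.375 + .625/.85)] = .140, a rise of about 5%. The 15%/15% bias is .017/.14 = 0.12 SE, and the 20%/10% bias is .060/.14 = 0.43 SE.

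**The case against.** The strongest reply is that silence is not prohibition. Nothing bars an assessment-only visit. The design overview says follow-up assessments will be obtained at 8 weeks, the questionnaires are done outside the therapy hour, and in the remote version a research assistant rather than the therapist sends the link. A reader might infer that people who leave therapy are barred from giving week-8 data. The documents do not say that, and the claim is limited to no documented route.

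A reader might also infer that any missed session costs an outcome. It does not: someone who misses session 2 or 6 but attends sessions 4 and 8 loses nothing, and a positive breath test allows one next-day reschedule.

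A third tempting reading is that week 8 becomes a comparison of therapy completers only. That goes too far. In the scenarios above 80–90% still attend, and FIML uses the stoppers' baseline and later data.

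Finally, the protocol expects no differential attrition and plans to look for it. Under equal stopping the illustrated bias is indeed small. What stands is that these checks are confined to baseline measures or left unspecified, so they could not reveal or correct loss related to drinking during treatment.

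**Conclusion.** The concern holds as a gap in documented outcome collection at weeks 4 and 8 for participants absent at those sessions. The lost week-8 HDD values cannot be recovered later, and the plan's all-randomised contrast then depends on missing at random where that assumption is least secure.

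The illustrated bias is about .02 SD with equal 15% stopping and about .06 SD with 20% MBRP and 10% RP stopping, against an SE of .14. It changes sign when RP loses sufficiently more people than MBRP. These sizes rest on assumed stopping rates, assumed worse drinking in stoppers, no effect in stoppers and full later follow-up.

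A reader might take the 45% figure as a forecast. It is a percentage of a small effect in the least favourable split examined, and the documents supply no rates to support it. Loss of precision is minor. The change is worth making because it is cheap and brings data collection into line with the stated analysis. The rule that drops participants after more than one missed session following positive breath tests is a separate matter.

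**What to change.** In Intermediate Session, End of Treatment and the corresponding COVID-19 procedures, state that the TLFB and self-report outcomes are sought from every randomised participant at weeks 4 and 8, whether or not therapy continues. For anyone who has not started therapy, count the due date from randomisation, because assignment precedes the goal-setting session and session 1.

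Extend the remote-survey option to both assessments. The week-20 email speaks of progress since finishing treatment, so these weeks need wording that suits people in or out of treatment.

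Split the existing $30 at weeks 4 and 8 into a part for the surveys and a part for the in-person components, as weeks 20 and 32 already separate surveys from blood. Paying all of it for surveys alone would leave nothing tied to the week-4 blood sample that feeds the Aim 3 mediators. Record the mode of completion.

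The cost is a short amendment and staff time to send links, since the surveys are already in Qualtrics. There are two downsides. Remote completers give no blood or neurocognitive data, and mode of completion will be associated with stopping therapy.
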